8.2.3 Electrocardiograms

An electrocardiogram (ECG) will be performed at timepoints as specified in the [SoA](#).

ECG will be taken in supine position, after the participant has been resting for at least 5 minutes. The assessment should be performed before interventions with the participant (eg, nasal endoscopy, blood draw).

The Investigator or authorised delegate will be responsible for the overall interpretation and determination of clinical significance of any potential ECG findings. In case of discrepancy between the Investigator's interpretation and that provided by the ECG machine (if applicable), the Investigator's interpretation will take precedence and should be noted on the printout and recorded in the eCRF. A copy of the ECG will be produced, and quality checked and kept in case of further need for re-evaluation.

It is highly recommended that the same machine is used for assessment throughout the participant's participation in the study. ECG evaluation will be recorded in the eCRF. ECG evaluation will be recorded in the eCRF.

8.2.4 Clinical Safety Laboratory Assessments

See [Table 12](#) for the list of clinical safety laboratory tests to be performed and the [SoA](#) for the timing and frequency. All protocol-required laboratory assessments, as defined in the table, must be conducted in accordance with the Laboratory Manual and the SoA. Fasting before blood draw is recommended but not mandatory.

Blood and urine samples for determination of clinical chemistry, haematology and urinalysis will be taken at the visits indicated in the SoA. The date and results will be recorded on the appropriate eCRF.

For information on how AEs based on laboratory tests should be recorded and reported, see Section [8.3.5](#).

The clinical chemistry, haematology and urinalysis will be performed at a central laboratory.

Additional (repeated or unscheduled) safety samples may be collected if clinically indicated at the discretion of the Investigator, for safety reasons or for technical issues with the samples.

The Investigator should assess the available results with regard to clinically relevant abnormalities. The laboratory results should be signed and dated and retained at site as source data for laboratory variables.

The following laboratory variables will be measured.

Table 12 Laboratory Safety Variables

Haematology/Hemostasis (whole blood)	Clinical Chemistry (serum or plasma)
B-Haemoglobin (Hb)	S-Alkaline phosphatase (ALP)
B-Leucocyte count	S-Alanine transaminase (ALT)
B-Leucocyte differential count (absolute count)	S-Aspartate transaminase (AST)
B-Platelet count	S-Bilirubin, total
B-Haematocrit	S-Blood urea nitrogen
B-Mean Corpuscular Volume	S-Calcium, total
B-Red blood cell (RBC) count ^a	S-Chloride
	S-Creatinine
Urinalysis (dipstick)	S-Creatinine kinase (CK)
U- Blood	S-CRP
U-Protein	S-Gamma-glutamyl transpeptidase (GGT)
U-Glucose	S-Glucose
U-Microscopy and culture as required ^b	S-Lipid Profile ^c
	S-Phosphorus
	S-Potassium
	S-Sodium
	S-Total Cholesterol
	S-Uric acid

^a The sponsor personnel involved in the analysis and conduct of the study and site will be blinded to the immunoglobulin, eosinophil, basophil and monocyte (both absolute and percentage) values from the central laboratory reports except screening visits (V1 and V2) and any repeat testing that is performed during the screening period and prior to Investigational Product (IP) administration at V3.

^b Urine sample will be analysed by urine dipstick at site and sent to the central laboratory only for analysis when a positive dipstick result for any parameter is observed.

^c Lipid profile consists of the following tests: Direct high-density lipoprotein cholesterol (HDL-C) 4th Generation, Triglycerides, Cholesterol, Low-density lipoprotein (LDL) cholesterol Friedewald 4th (calculation), Very-low-density lipoprotein (VLDL) cholesterol Friedewal (calculation).

NB. In case a participant shows an AST **or** ALT $\geq 3\times$ ULN together with total bilirubin $\geq 2\times$ ULN please refer to [Appendix E](#). Actions required in cases of increases in liver biochemistry and evaluation of Hy's Law', for further instructions.

8.2.4.1 COVID-19 Entry Screening Questionnaire

A COVID-19 screening questionnaire must be completed via telephone approximately within 72 hours prior to every study visit, regardless of the visit being on-site, at participant's home, or at an alternative location. Participant COVID-19 screening should include:

- Symptom history
- Exposure to someone diagnosed with COVID-19 in the past 14 days
- Recent travel including to countries with CDC Level 2 or higher travel warning or equivalent or known COVID-19 hot spots
- Unexplained fever, cough, shortness of breath, chills, muscle pain, headache, sore throat and/or new loss of taste or smell within the past 14 days

This questionnaire is to be conducted at minimum and local regulation and guidance should be followed.

Example of questionnaire:

- 1 Have you experienced unexplained fever, cough, shortness of breath, chills, muscle pain, headache, sore throat, and/or new loss of taste or smell within the past 14 days?
- 2 Have you been in contact with anyone who is sick or with symptoms (refer to question 1) in the last 14 days?
- 3 Have you been exposed to someone diagnosed with COVID-19 in the last 14 days?
- 4 Have you been practicing social distancing over the last 14 days? (refer to region/city/country regulations)
- 5 Have you travelled in the last 14 days, if so, where? (recent travel including to countries/regions with CDC Level 2 or higher travel warning or equivalent or known Covid-19 hot spots)
- 6 Have you been in isolation or quarantine for any reason in the past 14 days?
- 7 Have you been diagnosed with Covid-19 at any time, if so where and when?

Sites may use their own version of questionnaire per local guidance. Responses are not considered as part of clinical trial data and are not recorded in RAVE. The site will determine the appropriate course of action based on the responses to questionnaire. Participants who report symptoms should be referred for further evaluation as per investigator judgement. Visit should be cancelled or rescheduled, if needed as judged by Investigator.

8.2.4.2 SARS-CoV-2 Testing

Laboratory safety variables for SARS-CoV-2 testing are described in [Table 13](#).

At screening visit (V1), sites should perform testing for SARS-CoV-2 in line with local guidelines. Either a nasopharyngeal swab (PCR) test or a rapid antigen test are acceptable. PCR tests should be analysed at the central laboratory. Rapid antigen tests should be analysed locally and the results entered on the eCRF.

SARS-CoV-2 nasopharyngeal swab test and SARS-CoV-2 serology (collected at Visit 3) will be analysed at central laboratory. Instructions for sample collection, processing, storage, and shipment will be included in a separate laboratory manual provided to the sites. SARS-CoV-2 serology data will be used to assess individual AEs but will not be used for subgroup analyses (eg, serology positive/negative).

In case of re-screening due to previous screen failure because of a positive SARS-CoV-2 nasopharyngeal swab (PCR) test, a rapid antigen test should be performed locally at site instead of performing a repeat central laboratory nasopharyngeal swab (PCR) test (as long as this is acceptable with respect to local guidelines).

Table 13 SARS-CoV-2 Laboratory Safety Variables

Laboratory Test	Visit
SARS-CoV-2 nasopharyngeal swab test (or COVID-19 rapid test)	Visit 1
SARS-CoV-2 serology test	Visit 3

Sites should also follow local SARS-CoV-2 testing guidelines outside of CSP study assessments, if applicable.

8.2.4.3 Pregnancy Test

The following tests are applicable to female participants only and will be conducted in accordance with the schedules provided in the SoA.

- Serum β -human chorionic gonadotropin (β -HCG) – To be performed for all females at Visit 1 except for those who are NOT of childbearing potential as defined in inclusion criterion 8. This test is to be sent to and analysed at the central laboratory;
- FSH: To be performed at Visit 1 only, for female participants to confirm postmenopausal status in women < 50 years who have been amenorrhoeic for > 12 months;
- Urine HCG: To be performed at the study site or at home for all females at each treatment visit **before** IP administration using a dipstick except for those females who are NOT of childbearing potential as defined in inclusion criterion 8. A positive urine test result must be confirmed with serum β -HCG.

8.2.4.4 Serology

Hepatitis B surface antigen, hepatitis C antibody: To be performed only at screening; test to be performed at central laboratory.

HIV-1 and HIV-2 antibodies: To be performed only at screening; test to be performed at central laboratory.

Instructions for sample collection, processing, storage, and shipment can be found in a separate Laboratory Manual provided to the sites.

8.2.5 Other Safety Assessments

8.2.5.1 Weight and Height

Weight and height will be measured in accordance with schedules provided in the SoA.

The participant's weight will be recorded in kilograms; height will be recorded in centimetres. Weight and height measurements will be performed in light clothing and with shoes off.

8.2.5.2 Asthma Exacerbations (for Asthma/AERD/NSAID-ERD Participants Only)

During the study, an asthma exacerbation will be defined as a worsening of asthma that leads to any of the following:

- A temporary bolus/burst of systemic corticosteroids (or a temporary increase in stable OCS background dose) for at least 3 consecutive days to treat symptoms of asthma worsening; a single depo-injectable dose of corticosteroids will be considered equivalent to a 3-day burst of systemic corticosteroids.
- An emergency room or urgent care visit (defined as evaluation and treatment for < 24 hours in an emergency department or urgent care centre) due to asthma that required systemic corticosteroids (as per the above).
- An inpatient hospitalisation (defined as admission to an inpatient facility and/or evaluation and treatment in a healthcare facility for ≥ 24 hours) due to asthma.

In addition, participants are required to report any of the following in the eDiary:

- An increase in rescue medication use of 4 or more puffs on at least 2 consecutive days compared with the average use during baseline or use of 12 puffs/day on any one day, and/or;
- An additional nebulised β 2 agonist use on at least 2 consecutive days compared with the average use during baseline, and/or;

- An increase of 2 or more nights with awakenings due to asthma requiring rescue medication over a 7-day period compared with the average during baseline, and/or ≥ 6 out of previous 7 nights with awakenings due to asthma requiring rescue medication (this criterion should be met on 2 consecutive days).

If an exacerbation event is not associated with deterioration in at least 1 of the pre-specified objective measurements, the Investigator will have to justify the decision for defining the event as an exacerbation and record it in the eCRF. Events that are not supported by any objective assessment will be deemed not to be a protocol defined exacerbation.

The start of an exacerbation is defined as the start date of systemic corticosteroids or of a temporary increase in a stable OCS background dose, date of ER or urgent care visits requiring systemic corticosteroids, or date of hospital admission due to asthma, whichever occurs earlier.

The end date of an exacerbation is defined as the last date of systemic corticosteroids or of a temporary increase in a stable OCS background dose, date of ER or urgent care visit, or date of hospital discharge, whichever occurs later.

If less than 7 days have elapsed since the end date of an asthma exacerbation and the start date of a new asthma exacerbation, the second event will be considered a relapse of the prior asthma exacerbation.

See section [8.3.5](#) for additional information on recording asthma exacerbations as an AE/SAE during the study.

8.2.5.3 Nasal Polyp Exacerbations

During the study, nasal polyp exacerbation will be defined as a worsening of nasal polyp symptoms that leads to use of systemic corticosteroids or systemic antibiotics for at least 3 consecutive days or requires hospitalisation.

The start of nasal polyp exacerbation is defined as the start date of systemic corticosteroids/systemic antibiotics or hospitalisation whichever is earlier and the end date of nasal polyp exacerbation is defined as the last date of systemic corticosteroids/systemic antibiotics or hospitalisation whichever is later.

8.3 Adverse Events and Serious Adverse Events

8.3.1 Time Period and Frequency for Collecting AE and SAE Information

Adverse events and Serious Adverse Events will be collected from time of signature of informed consent form throughout the treatment period and including the follow-up period.

All SAEs will be recorded and reported to AstraZeneca or designee within 24 hours, as

indicated in [Appendix B](#). The Investigator will submit any updated SAE data to AstraZeneca within 24 hours of it being available.

If the investigator becomes aware of a serious adverse event with a suspected causal relationship to the investigational medicinal product that occurs after the end of the clinical study in a participant treated by him or her, the investigator shall, without undue delay, report the serious adverse event to the sponsor.

The method of recording, evaluating, and assessing causality of AE and SAE and the procedures for completing and transmitting SAE reports are provided in [Appendix B](#).

8.3.2 Follow-up of AEs and SAEs

After the initial AE/SAE report, the Investigator is required to proactively follow each participant at subsequent visits/contacts. All AEs and SAEs will be followed until resolution, stabilisation, the event is otherwise explained, or the participant is lost to follow-up.

Any AEs that are unresolved at the participant's last AE assessment or other assessment/visit as appropriate in the study are followed up by the investigator for as long as medically indicated, but without further recording in the eCRF. AstraZeneca retains the right to request additional information for any participant with ongoing AE(s)/SAE(s) at the end of the study, if judged necessary.

Adverse events variables

The following variables will be collected for each AE:

- AE (verbatim)
- The date and time when the AE started and stopped
- Maximum Intensity of the AE
- Whether the AE is serious or not
- Investigator causality rating against the Investigational Product(s) (yes or no)
- Action taken with regard to Investigational Product(s)
- AE caused participant's withdrawal from study (yes or no)
- Outcome

In addition, the following variables will be collected for SAEs:

- Date AE met criteria for SAE
- Date investigator became aware of SAE
- AE is serious due to (specify the SAE criteria per definition in [Appendix B](#))

- Date of hospitalisation
- Date of discharge
- Probable cause of death
- Date of death
- Autopsy performed
- Causality assessment in relation to study procedure(s)
- Causality assessment to other medication

8.3.3 Causality Collection

The investigator should assess causal relationship between Investigational Product and each AE, and answer ‘yes’ or ‘no’ to the question ‘Do you consider that there is a reasonable possibility that the event may have been caused by the investigational product?’

For SAEs, causal relationship should also be assessed for other medication and study procedures. Note that for SAEs that could be associated with any study procedure the causal relationship is implied as ‘yes’.

A guide to the interpretation of the causality question is found in [Appendix B](#) of the CSP.

8.3.4 Adverse Events Based on Signs and Symptoms

All AEs spontaneously reported by the participant or reported in response to the open question from the study site staff: ‘Have you had any health problems since the previous visit/you were last asked?’ or revealed by observation will be collected and recorded in the eCRF. When collecting AEs, the recording of diagnoses is preferred (when possible) to recording a list of signs and symptoms. However, if a diagnosis is known and there are other signs or symptoms that are not generally part of the diagnosis, the diagnosis and each sign or symptom will be recorded separately.

8.3.5 Adverse Events Based on Examinations and Tests

The results from the CSP mandated laboratory tests, vital signs and ECG will be summarised in the CSR. Deterioration as compared to baseline in protocol-mandated laboratory values/vital signs/ECG should therefore only be reported as AEs if they fulfil any of the SAE criteria or are the reason for discontinuation of treatment with the IP.

If deterioration in a laboratory value/vital sign/ECG is associated with clinical signs and symptoms, the sign or symptom will be reported as an AE and the associated laboratory result/vital sign will be considered as additional information. Wherever possible the reporting Investigator uses the clinical, rather than the laboratory term (eg, anaemia versus low haemoglobin value). In the absence of clinical signs or symptoms, clinically relevant

deteriorations in non-mandated parameters should be reported as AE(s).

Any new or aggravated clinically relevant abnormal medical finding at a physical examination as compared with the baseline assessment will be reported as an AE.

When collecting AEs, the recording of diagnoses is preferred, when possible, to recording a list of signs and symptoms. Asthma symptoms or signs, such as wheeze, cough, chest tightness, dyspnoea, breathlessness and phlegm, will be recorded as AEs only when:

- The sign or symptom is serious according to definitions, see [Appendix B](#)
- The participant discontinues IP due to the sign or symptom
- The sign or symptom is new to the participant or not consistent with the participant's pre-existing asthma history (defined as within 1 year of V1) as judged by the Investigator.

Asthma exacerbation should be recorded as an AE or SAE only if it fulfils any of the above criteria

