4 STUDY DESIGN

4.1 Overall Design

For an overview of the study design see Section 1.2, Figure 1. For details on treatment given during the study, see Section 6.1.1.

For details on what is included in the efficacy and safety endpoints, see Section 3.

This is a Phase 3, multicentre, randomised, double-blind, placebo-controlled, parallel-group, study to evaluate the efficacy and safety of repeat dosing of tezepelumab 210 mg SC versus placebo in participants with severe CRSwNP.

Approximately 400 participants will be randomised globally 1:1 to receive tezepelumab 210 mg or matching placebo.

Participants will be stratified by region, prior nasal polyp surgery and co-morbid asthma/aspirin-exacerbated respiratory disease (AERD)/nonsteroidal anti-inflammatory drug exacerbated respiratory disease (NSAID-ERD). Randomisation will be monitored to ensure that 50%-70% of the study population will have co-morbid asthma/AERD/NSAID-ERD, and at least 50% will have had prior surgery for CRSwNP. When the target percentage of participants in a stratum in a region is reached, consideration will be given to closing the IWRS randomisation for that subgroup, which may be done either overall or within a specific region. Once a subgroup is closed, participants in the screening/run-in period in the closed subgroup will not be allowed to be randomised and will be screen failed.

After enrolment, eligible participants will enter a screening/run-in period and will have their current INCS therapy standardised to Mometasone furoate (MFNS) or equivalent INCS at Visit 1 and throughout the screening and study period. Two doses of MFNS (50 μ g/actuation) in each nostril twice daily (total 400 μ g daily) or equivalent INCS will be administered unless there is a medical rationale to use the lower dose (QD) regimen. Equivalent dose should refer to the highest approved country INCS dose for CRSwNP.

In countries that receive standardised MFNS centrally, each participant will receive enough background medication to cover the need until the next on-site visit. For equivalent INCS, this may be provided per local guidelines or pharmacy card provided by sponsor. Intranasal corticosteroids dispensation will be performed according to the SoA (Table 1).

Intranasal corticosteroid compliance will be recorded by the participant in the ePRO diary and

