8.1.2.1 Nasal Polyposis Symptom Diary (NPSD) and Nasal Polyposis Symptom Screening Assessment (NPSSA)

The participant will complete an 11-item NP symptom diary (NPSD) each morning throughout the screening, treatment, and follow-up periods. The participant is asked to consider their experience with NP/nasal polyps over the past 24 hours when responding to each question. Participants are asked to report their experience with NP symptoms (nasal blockage, nasal congestion, runny nose, post-nasal drip (mucous drainage down the throat), headache, facial pain, facial pressure, and difficulty with sense of smell) and symptom impacts (difficulty with sleeping due to nasal symptoms and difficulty with daily activities due to nasal symptoms). Participants report the severity of each symptom and symptom impact at its worst using a 4-point verbal rating scale (0-None to 3-Severe). A total symptom score (TSS) is calculated by taking the sum of the 8 equally weighted symptom items. A single item to capture INCS compliance (yes or no) will be administered after the symptom and symptom impact items.

A 2-week recall version of the diary, the Nasal Polyposis Symptom Screening Assessment (NPSSA), will be used to evaluate minimum symptom criteria at Visit 1. This screening assessment has one additional item about consistency of symptoms over the past 12 weeks and omits the INCS compliance item.

The NPSD and NPSSA will be completed on the ePRO device per the SoA.

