8.8 Health Resource Utilisation

Health resource utilisation (HRU) and health economics data, associated with medical encounters, will be collected in the eCRF by the investigator and study site personnel for all participants throughout the study. Protocol-mandated procedures, tests, and encounters are excluded. At enrolment (V1), HRU information will be collected with a 'one year' recall period. At subsequent visits, HRU information will be collected with a recall period of 'since the last scheduled visit'. Overall, NP-specific and asthma specific HRU data will be collected.

The data collected may be used to conduct explanatory economic analyses and will include:

- Number and duration of medical care encounters, including surgeries, and other selected procedures (inpatient and outpatient), including type of surgery performed
- Duration of hospitalisation (total days or length of stay, including duration by wards [eg, intensive care unit])
- Visits
- Type of NP surgery
- Asthma-related and other reason procedures
- Number and type of diagnostic and therapeutic tests and procedures
- Outpatient participant medical encounters and interventions (including physician or emergency room visits, tests and procedures, and medications).

Use of systemic corticosteroids (oral, parenteral) for at least 3 days, an emergency room/urgent care visit with use of SCS or hospitalisation due to asthma should be recorded in the corresponding eCRFs.

Any hospitalisations for more than 24 hours should be reported as an SAE. Refer to Appendix [B 2](#) for reporting hospitalisation.

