### **4.2.10 Safety and Tolerability**

#### **4.2.10.1 Adverse Events**

All AE summaries will be presented by treatment group. AEs occurring during the screening/run-in period will be listed, but not summarised separately.

An overall summary table will be produced for the on-treatment and on-study periods showing the number and percentage of participants with at least one AE in each of the following categories: any AEs, SAEs, any AE with outcome death, and AEs leading to discontinuation of IP (DAEs). The total number of AEs in the different AE categories will also be presented. Key information of SAEs, AEs with outcome death, AEs leading to discontinuation of IP, and AESIs during the on-study period will be tabulated.

All AEs during the on-treatment and on-study periods will be summarised separately by SOC and PT assigned to the event using the MedDRA dictionary. An AE will be assigned into a period based on the onset date. For each PT, the number and percentage of participants reporting at least one occurrence of the event will be presented (ie, participants with multiple occurrences of the same PT will only be counted once).

Similar summaries by SOC and PT will be presented for the following during the on-treatment and on-study period:

- SAEs
- AE with outcome death
- AEs leading to discontinuation of IP (DAEs)
- Each AESI category separately
- The most common AEs (defined as those occurring in >3% of participants in either treatment group) – by PT only
- AEs by investigator's causality
- Each AESI category separately by investigator's causality

AEs are summarised by PT and maximum intensity during the on-treatment and on-study period. If a participant reports multiple occurrences of an AE within each PT, the maximum intensity will be taken as the highest recorded (the order being mild, moderate, and severe), respectively.

Exposure-adjusted AE (EAIR) summaries, and the difference in EAIR between treatment groups with 95% CIs calculated during the on-treatment and on-study period will be presented for each of the following summaries:

- overall AE categories: any AEs, SAEs, any AE with outcome death, and DAEs,
- All AEs by SOC and PT,
- SAEs by SOC and PT,

- DAEs by SOC and PT,
- Each AESI category by SOC and PT separately.

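### Asthma exacerbations are defined as a safety assessment, but the SAP plans no count or rate of them by arm, and non-serious ones that fit the participant's history and do not stop IP also stay out of the AE tables

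*Protocol*

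**What the plan says.** **Definition.** Protocol 8.2.5.2, under Other Safety Assessments, defines an asthma exacerbation as a worsening that leads to a course of SCS, an emergency or urgent care visit needing SCS, or inpatient admission. It sets start and end dates and treats a new event within 7 days as a relapse of the previous one.

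**Collection.** Protocol 8.8 covers SCS use, emergency or urgent care visits with SCS, and admission: "hospitalisation due to asthma should be recorded in the corresponding eCRFs". Under Protocol 7.1.1, telephone contacts after IP is stopped (follow-up options 2 and 3) also gather exacerbation information.

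**AE rule.** Protocol 8.3.5 gives three criteria for recording asthma signs and symptoms as AEs: the event is serious, it leads to stopping IP, or it is new or out of keeping with the asthma history of the year before Visit 1. It then adds: "Asthma exacerbation should be recorded as an AE or SAE only if it fulfils any of the above criteria".

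**SAP.** Section 4.2.10.1 says "All AEs during the on-treatment and on-study periods will be summarised separately by SOC and PT", with similar tables for SAEs, AEs leading to discontinuation and AESIs. Sections 3 and 4 contain no exacerbation variable, summary or model. Section 6, on changes from the protocol, does not mention the omission.

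**Confirmation of events.** Section 8.2.5.2 also states that "participants are required to report any of the following in the eDiary", followed by rescue puffs, nebuliser use and night awakenings compared with baseline. It adds: "Events that are not supported by any objective assessment will be deemed not to be a protocol defined exacerbation". Section 8.1.2.1 describes the daily diary: "The participant will complete an 11-item NP symptom diary (NPSD) each morning". Its items are eight nasal symptoms, two symptom impacts and INCS compliance.

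**The concern.** Start, end and relapse rules serve to count events, yet no count is planned. A participant with known asthma may have a typical exacerbation, take SCS as an outpatient and stay on IP. That event meets 8.2.5.2, need not be an AE under 8.3.5, and appears in no exacerbation summary in the SAP.

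At stake is a comparison by arm of a harm in at least half of the trial population, both on treatment and after it. The period after treatment matters because dosing ends at Week 48 while follow-up runs to Week 64 or 76, and other biologics are restricted after the last dose (Protocol 7.1.1 and Table 6).

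**Working it through.** The plan gives no expected number or rate of exacerbations, so there is no figure to reproduce. The check is mainly a tracing of the text.

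**1. Size of the subset.** Inputs from Protocol 4.1: "Randomisation will be monitored to ensure that 50%-70% of the study population will have co-morbid asthma/AERD/NSAID-ERD" and "Approximately 400 participants will be randomised globally 1:1 to receive tezepelumab 210 mg or matching placebo".
- 400 x 0.50 = 200 and 400 x 0.70 = 280 participants.
- Per arm: 200/2 = 100 to 280/2 = 140.

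**2. Where each type of exacerbation appears.**

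| Type under 8.2.5.2 | AE/SAE tables | Other analyses in the SAP |
|---|---|---|
| SCS course, outpatient, fits history, IP continued | Not required by 8.3.5 | A course in the SCS summaries to Week 52, pooled with other indications |
| Emergency or urgent care visit with SCS, fits history, IP continued | Not automatic: Appendix B 2 says emergency room treatment is not serious in itself, although intensive treatment for allergic bronchospasm is one of its examples of an important medical event | As above |
| Inpatient admission | Yes, as an SAE (8.8, Appendix B 2) | SAE tables |
| Any type that stops IP, or is new or out of keeping with history | Yes | AE tables |

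The first row, and part of the second, reach neither the AE tables nor a dedicated summary. Protocol 8.3.11 treats the disease under study the other way: NP events become reportable as AEs once they meet the NP exacerbation definition.

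**3. What the related analyses show.**
- ACQ-6 has a deterioration category and a control status (SAP 3.4.8, 4.2.8.6), but recalls one week at a few visits. FEV1 and FeNO are also visit measurements. None counts events between visits.
- SCS exposure is repeated for any reason and for reasons other than NP (SAP 3.4.5, 4.2.8.8). Time to first SCS is analysed for any reason (4.2.7.2.4). None isolates asthma, and all stop at Week 52.

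**4. After treatment.** With the last dose on its target day at Week 48 (Day 337), the on-treatment period ends at 337 + 33 = Day 370. The target days for Weeks 64 and 76 are 449 and 533 (SAP Table 1). This leaves 449 - 370 = 79 days, or 533 - 370 = 163 days for about the first 200 participants. In this window:
- there is no SCS analysis, only concomitant medication tables by drug;
- ACQ-6 and FEV1 depend on SAP 4.2.9.5, whose heading says Week 52 and whose text says Week 76, while SAP 6 says Week 52;
- FeNO is summarised to Week 76;
- Protocol 9.4.3 plans a separate post-treatment AE tabulation, but SAP 4.2.10.1 gives on-treatment and on-study tables, plus one for events after Week 64 in the Additional FU set.

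**5. Illustration on assumptions only.** Assume 0.1-0.5 exacerbations per participant over 52 weeks (not in the documents).
- Per arm: 100 x 0.1 = 10 to 140 x 0.5 = 70 events. Both arms: 20 to 140.
- Assume also that 5-20% are admitted and that no other AE criterion applies. Then 80-95% fall outside the AE tables: 20 x 0.80 = 16 to 140 x 0.95 = 133 events in both arms.

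These figures cover the treatment year only and do not size the post-treatment gap.

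**The case against.** The best case against the point is that asthma worsening is analysed by arm in several ways. Admissions reach the SAE tables, and the on-study tables include follow-up. FEV1 is a key secondary endpoint, ACQ-6 deterioration is summarised, and non-NP steroid use is tabulated. Exacerbations are not an objective or endpoint: the safety objective rests on AEs/SAEs, laboratory tests, vital signs and ECG. Health resource use, with asthma-specific encounters, is collected, and its analysis was moved to a separate exploratory plan not available here.

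Most of this stands, and it rules out three stronger readings that a reader might infer.
- **That asthma worsening goes unreported.** It does not; the analyses above report it in part.
- **That the AE rules leave out most exacerbations.** The documents give no rate and no split by type. Entry requires no exacerbation history, and SCS use within 3 months before Visit 1 is excluded. Investigators may therefore judge some SCS-treated events to be out of keeping with recent history and record them as AEs.
- **That the diary data do not exist, or that the definition cannot be applied.** EQ-5D-5L and WPAI are also completed on the eDiary (Protocol 8.1.2.3, 8.1.2.8), so the content of the NPSD does not settle what the eDiary holds. Section 8.2.5.2 never says which objective measurements it means. The documents show an inconsistency, not missing data.

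The objection does not supply a count. No analysis in the SAP isolates asthma exacerbations. Resource-use tables, if they exist, would count encounters rather than protocol-defined events.

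**Conclusion.** The point holds in a limited form. The SAP plans no count or rate by arm of protocol-defined asthma exacerbations in a subset of 200-280 participants. Those that are non-serious, fit the participant's history and do not stop IP are also left out of the AE tables. Related analyses show asthma worsening only in part. The post-treatment period is covered least, because the SCS analyses end at Week 52.

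The number of events affected cannot be derived from the documents; the ranges in the illustration depend wholly on assumed rates and admission shares. The 50-70% refers to asthma, AERD and NSAID-ERD combined. The conclusion about planned analyses covers this SAP, not the unseen exploratory plan. The co-primary and key secondary analyses are unaffected. This is a cheap improvement to the safety reporting.

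**What to change.** Add to SAP 4.2.10, for the co-morbid asthma/AERD/NSAID-ERD subset, by arm and separately for the on-treatment and post-treatment periods:
- the number and proportion of participants with at least one protocol-defined exacerbation;
- the exposure-adjusted rate.

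Use the eCRF-recorded data and the protocol's 7-day relapse rule. Assign events to periods by onset date, as for AEs. State whether participants are grouped by actual treatment, as in the other safety tables, because SAP 2.1.1 defines this subset by randomised treatment. The cost is one subsection and one or two tables, with no new data collection. SAP 2.1.4 rules out updates after the primary database lock; past that point, the tables can go in the CSR, labelled as added.

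Separately, reconcile Protocol 8.2.5.2 (the eDiary asthma items and the unspecified objective measurements), 8.1.2.1, 8.3.5 and the Schedule of Activities, so that it is clear which data support an exacerbation and where they are collected. Which clinical rule should apply is for the sponsor to decide. The cost is a wording correction.
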